10.2 Follow-up Reporting by the Investigator

The AE CRF completed initially must be updated within 24 hours after the Investigator has become aware of any new relevant information concerning the SAE (e.g., outcome, precise description of medical history, results of the investigation). All relevant information must be included directly in the AE CRF and the appropriate Safety Complementary Information CRFs. An e-mail alert will be sent automatically to the GPV Department and to the CRA. Copies of documents (e.g., medical records, discharge summary, autopsy) may be requested by the GPV Department.

The anonymity of the subject must always be respected when forwarding this information.

10.3 Reporting of SAEs Occurring After a Subject Has Completed the Study

Any SAE that occurs after a subject has completed the study but that is likely to be related to the investigational product(s), other products (e.g., a benefit vaccine), or to the experiment must also be reported as soon as possible. In such a case, the reporting procedure to be followed is identical to that described in [Section 10.1](#).

10.4 Assessment of Causality

The causal relationship between the SAE and the product administered will be evaluated by the Investigator as described in [Section 9.3.2.3.5](#).

Following this, the Sponsor's Pharmacovigilance (PV) Global Safety Expert will also assess the causal relationship to the product, based on the available information and current medical knowledge.

The causal relationship to study procedures will be also assessed in the CRB.

The decision to modify or discontinue the study may be made after mutual agreement between the Sponsor and the Investigator(s).

10.5 Reporting SAEs to Health Authorities and IECs / IRBs

The Sponsor will inform the relevant health authorities of any reportable SAEs according to the local regulatory requirements. Reporting to the health authorities will be according to the Sponsor's standard operating procedures.

The Sponsor's RMO [REDACTED] will notify the Investigators in writing of the occurrence of any reportable SAEs. The Investigators / Sponsor will be responsible for informing the IECs or IRBs that reviewed the study protocol.

11 Data Collection and Management

11.1 Data Collection and CRB Completion

Individual diary cards, specifically designed for this study by the Sponsor and provided to the study sites, will be given to study participants for the recording of daily safety information as described in [Section 9.3.2.3](#). These diary cards will include prelisted terms and intensity scales (see [Table 9.1](#) and [Table 9.2](#)) as well as areas for free text to capture additional safety information or other relevant details. Parents / legally acceptable representatives will also be provided with rulers for measuring the size of injection site reactions, and with standard digital thermometers for measuring daily temperatures. To ensure consistency of reporting, the study sites will instruct parents / legally acceptable representatives on how to correctly use these tools.

At specified intervals, the Investigator or an authorized designee will interview the parents / legally acceptable representatives to collect the information recorded in the diary card, and will attempt to clarify anything that is incomplete or unclear. All clinical study information gathered by the study site will be reported electronically by the Investigator or authorized designee using a web-based CRB. (Any information that was not documented in the diary card will first be captured in the source document and then reported electronically.) The CRB has been designed specifically for this study under the responsibility of the Sponsor, using a validated Electronic Records / Electronic Signature-compliant platform (21 CFR Part 11).

To ensure the correct and consistent completion of the CRBs, the Sponsor or authorized representative will provide all necessary tools, instructions, and training to all site staff involved in data entry prior to study start. Additional instructional documents such as training manuals and completion instructions will be provided to assist with data entry during the course of the study.

Upon completion of training, each user requiring access to the EDC system will be issued a unique username and password. In the event of a change in study personnel, each newly assigned individual will receive a unique username and password; the username and password of a previous user may not be reissued. If any study personnel leave the study, the Investigator is responsible for informing the Sponsor immediately so that their access is deactivated. An audit trail will be initiated in the EDC system at the time of the first data entry to track all modifications and ensure database integrity.

The Investigator is responsible for the timeliness, completeness, and accuracy of the information in the CRBs; must provide explanations for all missing information; and must sign the CRB using an e-signature.

11.2 Data Management

Management of SAE Data

During the study, SAE data (reported on the AE, and Safety Complementary Information CRFs) will be integrated into the Sponsor's centralized GPV database upon receipt of these forms and after a duplicate check. Each case will be assigned a case identification number. Each case will be assessed by the case management platform or its delegate before being reported to the relevant authorities as necessary. The assessment of related cases will be done in collaboration with the PV Global Safety Expert and the RMO. Follow-up information concerning a completed case will be entered into the GPV database, and a new version of the case will be created.

The information from the GPV database cases will be reconciled with that in the clinical database.

Management of Clinical and Laboratory Data

Clinical data, defined as all data reported in the CRB, and laboratory data will be handled by the Sponsor's Clinical Data Management (CDM) platform or authorized representative.

During the study, clinical data reported in the CRBs will be integrated into the clinical database under the responsibility of the Sanofi Pasteur CDM platform. Data monitoring at the sites and quality control in the form of computerized logic and / or consistency checks will be systematically applied to detect errors or omissions. In addition, data reviews may be performed several times by the Sponsor's staff in the course of the study. Any questions pertaining to the reported clinical data will be submitted to the investigator for resolution using the EDC system. Each step of this process will be monitored through the implementation of individual passwords to maintain appropriate database access and to ensure database integrity.

The validation of the immunogenicity data will be performed at the laboratory level following the laboratory's procedures. Information from the laboratory will be checked for consistency before integration into the clinical Datawarehouse.

After integration of all corrections in the complete set of data, and after the SAE information available from CDM and the GPV Department has been reconciled, the database will be released for statistical analysis.

11.3 Data Review

A review of the data is anticipated through the data review process led by Data Management before database lock. The safety of the investigational product will be continuously monitored by the Sponsor. Periodic safety data review will be performed by the Sponsor's SMT.

12 Statistical Methods and Determination of Sample Size

12.1 Statistical Methods

Clinical data will be analyzed under the responsibility of the Biostatistics Platform of the Sponsor. A SAP will be written and peer reviewed before any analyses. In accordance with the protocol, the SAP will describe all analyses to be performed under the responsibility of the Sponsor and all the conventions to be taken.

12.1.1 Hypotheses and Statistical Methods for Primary Objective

12.1.1.1 Hypotheses

Thirty days after the administration of MenACYW conjugate vaccine alone or concomitantly with Bexsero[®] in the second year of life (at Visit 5), the percentage of subjects who achieve hSBA titers $\geq 1:8$ for meningococcal serogroups A, C, W, and Y in Group 1 are non-inferior to the corresponding percentages in Group 2.

Null hypothesis (H_0): $p_{(G1)} - p_{(G2)} \leq -10\%$

Alternative hypothesis (H_1): $p_{(G1)} - p_{(G2)} > -10\%$

where $p_{(G1)}$ and $p_{(G2)}$ are the percentages of subjects who achieve hSBA titers $\geq 1:8$ in Group 1 and Group 2, respectively. Each of the serogroups A, C, W, and Y will be tested separately. If the lower limit of the 2-sided 95% confidence interval (CI) of the difference between the 2 proportions is $> -10\%$, the inferiority assumption will be rejected.

12.1.1.2 Statistical Methods

For the 4 non-inferiority hypotheses using the vaccine response rates, the 95% CI of the difference in proportions between Group 1 and Group 2 will be computed using the Wilson Score method without continuity correction (48).

The overall non-inferiority of primary objective will be demonstrated if all 4 individual null hypotheses are rejected.

12.1.2 Hypotheses and Statistical Methods for Secondary Objective

12.1.2.1 Hypotheses

No hypotheses will be tested. Descriptive statistics will be presented.

12.1.2.2 Statistical Methods

Descriptive statistics will be provided for the antibody titers against meningococcal serogroups A, C, W, and Y for Group 1 and Group 2. In general, categorical variables will be summarized and presented by frequency counts, percentages, and CIs. The 95% CIs of point estimates will be calculated using the normal approximation for quantitative data and the exact binomial distribution (Clopper-Pearson method) for percentages (49). For GMTs, 95% CIs of point estimates will be calculated using normal approximation assuming they are log-normally distributed.

Reverse cumulative distribution curve (RCDC) figures will be provided for the antibody titers against meningococcal serogroups A, C, W, and Y.

Secondary Objective 1 – Geometric mean titer ratio (GMTR) between Group 1 and Group 2 after the second dose of MenACYW conjugate vaccine:

Thirty days after the administration of MenACYW conjugate vaccine alone or concomitantly with Bexsero[®] in the second year of life (at Visit 5), the hSBA GMTR between Group 1 and Group 2 for meningococcal serogroups A, C, W, and Y will be calculated and 95% CI will be provided.

Assuming that \log_{10} transformation of the data follows a normal distribution, the \log_{10} (data) will be used for the statistical analysis, then antilog transformations will be applied to the results of calculations, in order to provide the results in terms of GMTRs.

For each of the GMTRs, the statistical methodology will be based on the use of the 2-sided 95% CI of difference in means of post-vaccination \log_{10} transformed concentrations between the 2 groups with normal approximation.

Secondary Objective 2 - Antibody responses of the first and second dose of MenACYW conjugate vaccine:

Descriptive analyses on A, C, W, and Y serogroups for all subjects in Group 1 and Group 2 providing a blood sample at corresponding time points (Visit 2, Visit 3, Visit 4 and Visit 5) using hSBA will include but not be limited to:

- GMT and 95% CI
- Titer distribution and RCDC
- Percentage of subjects with titer $\geq 1:4$ and $\geq 1:8$ and 95% CI
- Percentage of subjects with titer ≥ 4 -fold rise from pre-vaccination to post-vaccination, and 95% CI

- Percentage of subjects with hSBA vaccine seroresponse^a

Descriptive analyses on A, C, W, and Y serogroups for a subset of subjects in Group 1 and Group 2 providing a blood sample at corresponding time points (Visit 2, Visit 3, Visit 4, and Visit 5) using rSBA will include but not be limited to:

- GMT and 95% CI
- Titer distribution and RCDCs
- Percentage of subjects with titer $\geq 1:8$ and $\geq 1:128$ and 95% CI
- Percentage of subjects with titer ≥ 4 -fold rise from pre-vaccination to post-vaccination, and 95% CI
- Percentage of subjects with rSBA vaccine seroresponse^b

Secondary Objective 3 – Antibody persistence after the first dose of MenACYW conjugate vaccine:

To evaluate antibody persistence after the first dose of MenACYW conjugate vaccine administered at 3 months of age, descriptive analyses on A, C, W, and Y serogroups for all subjects in Group 1 and Group 2 providing a blood sample at Visit 3 and Visit 4 using hSBA will include but not be limited to:

- GMT and 95% CI
- Percentage of subjects with titer $\geq 1:4$ and $\geq 1:8$ and 95% CI

To evaluate antibody persistence after the first dose of MenACYW conjugate vaccine administered at 3 months of age, descriptive analyses on A, C, W, and Y serogroups for a subset of subjects in Group 1 and Group 2 providing a blood sample at Visit 3 and Visit 4 using rSBA will include but not be limited to:

- GMT and 95% CI
- Percentage of subjects with titer $\geq 1:8$ and $\geq 1:128$ and 95% CI

^a hSBA vaccine seroresponse for serogroups A, C, Y, and W is defined as:

- For a subject with a pre-vaccination titer $< 1:8$, the post-vaccination titer must be $\geq 1:16$.
- For a subject with a pre-vaccination titer $\geq 1:8$, the post-vaccination titer must be ≥ 4 -fold greater than the pre-vaccination titer.

^b rSBA vaccine seroresponse for serogroups A, C, Y, and W is defined as:

- For a subject with a pre-vaccination titer $< 1:8$, the post-vaccination titer must be $\geq 1:32$.
- For a subject with a pre-vaccination titer $\geq 1:8$, the post-vaccination titer must be ≥ 4 -fold greater than the pre-vaccination titer.

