5.1 Description of the Overall Study Design and Plan

5.1.1 Study Design

This study is a Phase III, open-label, randomized, parallel-group, active-controlled, multi-center study to evaluate the immunogenicity and describe the safety of MenACYW conjugate vaccine when administered concomitantly with a meningococcal group B vaccine (Bexsero[®]) and other routine pediatric vaccines as part of the National Immunization Schedule in healthy infants and toddlers in the UK.

Approximately 800 healthy infants aged ≥ 56 to ≤ 89 days (approximately 2 months of age) will be randomized 2:2:1 to the following 3 groups:

Group 1: MenACYW conjugate vaccine at 3 months and at 12 to 13 months of age; Bexsero[®] at 2, 4, and 12 to 13 months of age

Group 2: MenACYW conjugate vaccine at 3 months and at 12 to 13 months of age; Bexsero[®] at 2 and 4 months of age

Group 3: Bexsero[®] at 2, 4, and 12 to 13 months of age

Routine pediatric vaccines will be given to subjects in all groups according to the UK immunization schedule:

- Infanrix hexa[®] (Combined Diphtheria-Tetanus-acellular Pertussis [DTPa], Hepatitis B, Inactivated Poliovirus and *Haemophilus influenzae* type b Vaccine; DTPa-HBV-IPV+Hib) at 2, 3, and 4 months of age
- Rotarix[®] (rotavirus vaccine; RV) at 2 and 3 months of age
- Prevenar 13[®] (pneumococcal 13-valent conjugate vaccine; PCV13) at 2 and 4 months of age

The routine vaccines (Infanrix hexa[®], Rotarix[®], and Prevenar 13[®]) will be sourced by the investigators and administered as per the standard practices. MenACYW conjugate vaccine and Bexsero[®] will be provided by the Sponsor.

The routine pediatric vaccines administered in the second year of life (Menitorix[®], Priorix[®]/M-M-RVAXPRO[®], and PCV13 [for all groups], and Bexsero[®] [for Group 2]) may be given as per standard of care at the last study visit after completion of study procedures (Visit 5 at 13 to 14 months). For Group 2, Bexsero[®] will be provided by the Sponsor to complete the vaccination series for subjects enrolled in this group. Subjects in Group 3 will be offered a single dose of the licensed ACWY conjugate meningococcal vaccine (Nimenrix[®]). This is a non-study vaccine to be administered 30 days after the last study visit (Visit 5) at an additional optional visit, and will be outside the scope of the study evaluations. No immunogenicity and safety data will be collected after the administration of these vaccines.

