Note: Each visit may be conducted at the site (site visit) or at the subject's home (home visit).

Blood Sampling

Subjects will provide the following blood samples:

- Groups 1 and 2: 160 subjects in each group will be randomized to have 3 blood draws at the intervals mentioned below. The remaining subjects will only have 1 blood draw at Visit 5.
- Group 3: all 160 subjects will have 3 blood draws.

For the subjects randomized to have 3 blood draws in Group 1 and Group 2, the first 2 blood draws will be performed in a staggered way – approximately half of the subjects (~70 subjects in each group) will have blood draws at Visit 2 and Visit 3 (subset A), and the remaining half (~90 subjects in each group) will have blood draws at Visit 3 and Visit 4 (subset B). The third blood draw will be performed at Visit 5 for all subjects.

Subset A (~70 subjects in each group):

- a pre-vaccination blood sample at Visit 2
- a blood sample at Visit 3 (30 days after vaccination at Visit 2)
- a blood sample at Visit 5 (30 days after vaccination at Visit 4)

Subset B (~90 subjects in each group):

- a blood sample at Visit 3 (30 days after vaccination at Visit 2)
- a pre-vaccination blood sample at Visit 4
- a blood sample at Visit 5 (30 days after vaccination at Visit 4)

For the subjects randomized to Group 3, the first 2 blood draws will be performed in a staggered way – approximately half of the subjects (~70 subjects) will have blood draws at Visit 2 and Visit 3 (subset A), and the remaining half (~90 subjects) will have blood draws at Visit 3 and Visit 4 (subset B). The third blood draw will be performed at Visit 5 for all subjects.

Subset A (~70 subjects):

- a pre-vaccination blood sample at Visit 2
- a blood sample at Visit 3 (30 days after vaccination at Visit 2)
- a blood sample at Visit 5 (30 days after vaccination at Visit 4)

Subset B (~90 subjects):

- a blood sample at Visit 3 (30 days after vaccination at Visit 2)
- a pre-vaccination blood sample at Visit 4
- a blood sample at Visit 5 (30 days after vaccination at Visit 4)

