6.1.1.3 Dose Selection and Timing

- Subjects in Group 1 will receive 2 doses of MenACYW conjugate vaccine administered concomitantly with routine pediatric vaccines (1st dose at 3 months of age) or with Bexsero[®] (2nd dose at 12 to 13 months of age).
- Subjects in Group 2 will receive 2 doses of MenACYW conjugate vaccine administered concomitantly with routine pediatric vaccines (1st dose at 3 months of age) or alone (2nd dose at 12 to 13 months of age).

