6.1.2.3 Dose Selection and Timing

- Subjects in Group 1 will receive 3 doses of Bexsero[®] administered at 2, 4 and 12 to 13 months of age.
- Subjects in Group 2 will receive 2 doses of Bexsero[®] administered at 2 and 4 months of age. (Note: The 3rd dose of Bexsero[®] will be given at 13 to 14 months of age [Visit 5] after completion of study procedures, and will be provided by the Sponsor in order to complete the vaccination series).
- Subjects in Group 3 will receive 3 doses of Bexsero[®] administered at 2, 4 and 12 to 13 months of age.

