12.2.2.4 Safety Analysis Set for Vaccination at 4 Months of Age (SafAS3)

The SafAS3 for vaccination at 4 months of age is defined as those subjects who have received at least one dose of the study vaccines at Visit 3 around 4 months of age and have any safety data available. All subjects will have their safety analyzed after Visit 3 dose according to the vaccines they actually received at Visit 2 and Visit 3. For subjects who received Bexsero[®] vaccine and at least one dose of routine vaccines at Visit 3, who received MenACYW conjugate vaccine and at least one dose of routine vaccines at Visit 2 will be analyzed under “Group 1 + Group 2” combined group, while subjects who received Bexsero[®] and at least one dose of routine vaccines at Visit 3 but only received at least one dose of routine vaccines without MenACYW conjugate vaccine at Visit 2 will be analyzed under “Group 3”.

The subjects received at least one dose of study vaccines but out of the planned vaccination schedule at Visit 3 will be classified to “Other” group. The safety analysis tables will not present data for ‘Other’ group at Visit 3, and the safety data for ‘Other’ group at Visit 3 will be listed only.

Safety data recorded for a vaccine received out of the protocol design at Visit 3 will be excluded from the analysis (and listed separately).

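### Groups 1 and 2 share one regimen until the Visit 4 vaccination, so a named combined estimate would sharpen the dose-1 and persistence results at almost no cost

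*Protocol*

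**What the plan says.** The two groups are treated alike until Visit 4:

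- **Bexsero** (Section 6.1.2.3): "Subjects in Group 1 will receive 3 doses of Bexsero[®] administered at 2, 4 and 12 to 13 months of age" and "Subjects in Group 2 will receive 2 doses of Bexsero[®] administered at 2 and 4 months of age". The schedules first differ at 12 to 13 months.
- **First MenACYW dose** (Section 6.1.1.3): both groups receive "MenACYW conjugate vaccine administered concomitantly with routine pediatric vaccines (1st dose at 3 months of age".
- **Routine vaccines** (Section 5.1.1): "Routine pediatric vaccines will be given to subjects in all groups according to the UK immunization schedule".
- **Blood draws** (Section 5.1.1): in Groups 1 and 2, "160 subjects in each group will be randomized to have 3 blood draws". About 70 of these are sampled at Visits 2 and 3 (subset A) and about 90 at Visits 3 and 4 (subset B). The Visit 4 draw is taken before vaccination.

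For the secondary objectives, Section 12.1.2.2 opens with "Descriptive statistics will be provided for the antibody titers against meningococcal serogroups A, C, W, and Y for Group 1 and Group 2". Objective 3 (persistence) is analysed "for all subjects in Group 1 and Group 2 providing a blood sample at Visit 3 and Visit 4 using hSBA". Objective 2 uses the same pairing of groups for Visits 2 to 5. The lists of summaries are open-ended, and Section 12.1.2.1 states that no hypotheses are tested.

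A combined group is written out in one place only. For safety after Visit 3 (Section 12.2.2.4), infants "who received MenACYW conjugate vaccine and at least one dose of routine vaccines at Visit 2 will be analyzed under" a joint Group 1 + Group 2 heading. No counterpart exists for immunogenicity. Section 12.2.4 analyses the full analysis set by randomised group.

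**The concern.** Up to and including the pre-dose Visit 4 sample, Groups 1 and 2 are two randomised portions of one regimen. Response to the infant dose and its persistence to 12 months are therefore one quantity per serogroup and assay, not two. Section 12.1.2.2 does not say whether one estimate or two is intended.

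The per-group reading is the natural one. Under Objective 2 a single phrase covers Visits 2 to 5, and at Visit 5 the groups have been treated differently, so pooling there would make no sense. Where the authors want a combined group, as in Section 12.2.2.4, they say so.

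On that reading, each named secondary result appears as two less precise estimates of the same parameter, with nothing to say which is the result. This matters most where the subsets are small: Visit 2, Visit 4, and possibly rSBA at Visit 4.

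**Working it through.** **The plan's own figures.** The protocol gives no precision or power figure for Secondary Objectives 2 and 3. Its evaluable count for the primary objective reproduces: 320 × 0.70 = 224 per group (Section 12.5). So does the overall power in Table 12.1: 0.959 × 0.925 × 0.998 × 0.998 = 0.8835, against 88.4% stated. Neither is touched by this point.

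**Inputs.**
- Planned hSBA draws per group: 70 at Visit 2, 160 at Visit 3 (70 + 90), 90 at Visit 4 (Section 5.1.1).
- Loss: 30% (Section 12.5), assumed here to fall evenly on the subsets and visits.
- Interval method for percentages: Clopper-Pearson, 95% (Section 12.1.2.2).
- Response rates: 25%, 50% and 90%, all illustrative. The 25% is the MET39 figure for serogroups Y and W after a single dose at 6 months (Section 1.2.1.1), a different age from this trial.

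**Evaluable numbers.**
- Visit 2: 70 × 0.70 = 49 per group, 98 pooled.
- Visit 3: 160 × 0.70 = 112 per group, 224 pooled.
- Visit 4: 90 × 0.70 = 63 per group, 126 pooled.

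**Interval width.** For x responders among n, the lower limit is the 2.5% quantile of Beta(x, n − x + 1) and the upper limit is the 97.5% quantile of Beta(x + 1, n − x). Take x as the nearest whole number to rate × n. At Visit 4 and 50%, x = 32 of 63 gives 37.9% to 63.6%, a width of 25.7 points. Pooled, x = 63 of 126 gives 41.0% to 59.0%, a width of 18.1 (before rounding the limits).

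| Sample (30% loss) | Rate | Per-group width | Pooled width | Ratio |
|---|---|---|---|---|
| Visit 2, 49 vs 98 | 50% | 29.2 | 20.5 | 1.42 |
| Visit 3, 112 vs 224 | 50% | 19.2 | 13.5 | 1.42 |
| Visit 4, 63 vs 126 | 25% | 22.7 | 15.9 | 1.43 |
| Visit 4, 63 vs 126 | 50% | 25.7 | 18.1 | 1.42 |
| Visit 4, 63 vs 126 | 90% | 16.0 | 11.4 | 1.40 |

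With no loss at all, Visit 4 at 50% gives 21.5 (n = 90) against 15.1 (n = 180). The absolute widths shrink but the ratio stays at 1.42.

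**Geometric mean titres.** The log-scale interval width is proportional to 1/√n. Doubling n multiplies it by 1/√2 = 0.71, so it is about 29% narrower whatever the standard deviation.

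**rSBA at Visit 4.** Section 9.2.2.2 tests the first 100 infants per group randomised to three draws. The footnotes to Table 5.1 call subset A the first ~70 and subset B the last ~90. If enrolment follows that order (an assumption), only 100 − 70 = 30 per group have a Visit 4 rSBA sample, or 30 × 0.70 = 21 after loss. At about 50%, the exact interval is 44.5 points wide per group (10 of 21: 25.7% to 70.2%) and 31.6 points pooled (21 of 42).

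**The case against.** The case for leaving the text alone has real weight.

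- **The wording is neutral.** No sentence says that the groups are summarised separately, and the open-ended lists leave room for a pooled column. The SAP, which is not shown, may add one. This stands: the per-group reading is an inference, though the better-supported one.
- **Nothing is discarded.** A reader might infer that half the sample is given up. It is not: every planned sample in both groups is tested and reported, and a pooled percentage can be recovered from the two groups' counts. Only the precision of each displayed estimate suffers.
- **No decision depends on it.** These objectives are descriptive, with no test, power or success criterion. This stands.
- **SafAS3 is not a true parallel.** A reader might see a contradiction between the safety and immunogenicity sections. SafAS3 classifies infants by the vaccines received at Visits 2 and 3, which cannot separate Group 1 from Group 2, so the joint heading follows from that rule. The full analysis set follows randomisation. Section 12.2.2.4 shows only that the protocol spells out a combined group when one is meant.
- **A gap before Visit 4 is not strictly chance.** That would hold for all randomised infants. The main analyses use per-protocol sets, selected after randomisation in an open-label trial, so exclusions could differ by group. By-group results would help reveal this, which is a good reason to keep them.
- **The 30% loss is a whole-study figure** and probably overstates attrition at Visits 2 and 3. The ratio of about 1.4 hardly depends on it.

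**Conclusion.** This is an inexpensive improvement, not an error or an inconsistency. Before the Visit 4 vaccination the two groups estimate the same quantities, and the protocol names no combined immunogenicity estimate for them. Relying on per-group results makes the intervals about 1.4 times as wide as they need be, for example 25.7 against 18.1 points for hSBA at Visit 4 with a 50% rate.

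The absolute widths rest on an even 30% loss and illustrative response rates. The Visit 4 rSBA figures also rest on subset A having been enrolled first. The gain in precision is unbiased if per-protocol exclusions do not differ materially by group. The primary objective and every Visit 5 comparison are unaffected.

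**What to change.** In Section 12.1.2.2, under Secondary Objectives 2 and 3, state that:

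1. The main summary of dose-1 response and persistence is a combined Group 1 + Group 2 estimate at Visits 2, 3 and pre-dose Visit 4, for both hSBA and rSBA, on the matching per-protocol set.
2. By-group results for those visits are shown alongside, with the numbers excluded per group, to show comparability before the second dose and any differential exclusion.
3. Visit 5 results, and seroresponse and fold rise after the second dose, remain by group.

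The cost is one short paragraph and one added table column. No new samples, assays or subjects are needed. Making the change before the immunogenicity data are seen avoids a later choice of which estimate to feature.
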